#### 4.4 Sample size calculation

This sample size calculation is conservatively based on the ability to detect at least a moderate effect of Cohen's  $d = .50$  on the primary outcomes at follow-up (T3). A power analysis was conducted with G\*power. The analysis was conducted with a moderate effect size of 0.5, a  $\beta$ -power of .8, a p-value of 5%, and an independent two-sided t-test as method of analysis. This analysis showed that 64 patients need to be included in each condition. This means that a total of 128 patients needs to be included. Accounting for a drop-out of 20%, the goal for inclusion is set at a total of 154 patients. It is important to note that participants in the experimental condition are considered as a 'drop-out' when they don't fill out the questionnaires at all measuring moments, not when they stop using the intervention. In other words: patients can stop using the intervention. In other words: patients can stop using the intervention, but can still complete their participation in the study if they fill out all questionnaires. Adherence to the intervention is not the same as drop-out from the study, since it is a different concept. The main reason for this is that earlier research has shown that patients often stop using these interventions before all lessons are completed, so it is not realistic to expect that all patients fully complete the intervention. In order to account for this, the number of completed lessons will be included as a moderator for effectiveness in the analyses to investigate whether adherence is related to effectiveness. Additionally, a sub-goal of this study is to determine whether engagement is a predictor of adherence and effectiveness to incorporate non-adherence to the intervention in the study. The intended 154 patients will be included at four different organizations that all have multiple forensic outpatient clinics.

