## 8. METHODS

### 8.1 Study parameters/endpoints

In this study, multiple types of data are collected to answer the six research questions. First, a short overview will be provided, after which the specific measurement instruments will be explained in more detail.

The variables for the first research objective – focused on the improvement in regulatory emotional self-efficacy, treatment readiness and aggression – will be collected via short, validated self-report questionnaires that will be administered via Qualtrics. To answer the first research question, three primary outcome measures will be used. The main reason for selecting three outcome measures, is that this is the first RCT on internet-based interventions in forensic outpatient care [16]. Consequently, there are no other RCTs on which the choice for outcome measures can be based. The three main outcome measures are based on qualitative research, combined with insights of therapists and researchers [17, 19, 21, 42]. However, based on these sources, it is not clear which of these outcome measures is best to identify change on the short and long term due to the intervention. The intervention is viewed as potentially effective if the experimental group improves more than the control group on at least one of the outcome measures on T1, T2, and/or T3. The intervention is viewed as effective in case of changes on all three outcome measures on T3.

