## 10. STATISTICAL ANALYSIS

### 10.1 Primary study parameter(s)

Data will be analysed using IBM SPSS software (version 24.0) and significance was accepted at 0.05 or lower. Analyses will be done on intention to treat (ITT) basis.

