#### ***Determining effectiveness***

In order to determine whether the internet-based intervention Aggression is effective, multiple scenarios are possible.

First of all, it is possible that the scores of the experimental groups do not increase more than those of the control group on all three primary outcome measures at all measurement points (T1, T2 and T3). In that case, the intervention is viewed as ineffective. Second, there might be a significant improvement of the experimental group compared to the control group on one or more of the outcome measures on T1 (so halfway the intervention), but not on T2 and T3. This indicates that the intervention shows some promise, but cannot be viewed as effective. Further research on why the effects are not maintained until the end of the intervention and on the long term is then warranted. These questions will be partly answered by means of the interviews at T3. Third, there might be a change on T2 - so directly after completing the intervention - on one or more of the outcome measures in the experimental group compared to the control group, which is not maintained at T3. In that case, the intervention is viewed as promising and potentially useful for clinical practice because participants did experience benefits, but not effective because the effects are not maintained on the long term. In that case, future research into why these effects are not maintained and what this means for the usefulness of these interventions in forensic outpatient care is necessary. Fourth, there might be an improvement of the experimental group compared to

the control group on T3 on one or two outcome measures. In that case, the intervention is viewed as effective since it leads to benefits on the long term. However, future research is again warranted to investigate why these changes did not occur on the other outcome measure(s). Finally, if the experimental group outperforms the control group on all three outcome measures at T3, the conclusion will be that the intervention is effective and no future research is warranted. However, this of course does not mean that future research is not desirable for the sake of replicability.

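### Sections 8.1 and 10.1 define an effective intervention differently, and the one-of-three rule at T3 has no stated correction across outcomes: a false positive verdict in up to 7.3% of cases against 2.5% for one outcome

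*Combined protocol and SAP*

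**What the plan says.** **Threshold.** Section 10.1 opens with one level for everything: "significance was accepted at 0.05 or lower".

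**Verdict rule in 10.1.** Determining effectiveness lists several scenarios. The fourth concerns an improvement of the experimental arm relative to "the control group on T3 on one or two outcome measures. In that case, the intervention is viewed as effective". The last scenario, superiority on all three at T3, is also called effective.

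**Verdict rule in 8.1.** Effective is kept for changes on all three outcomes at T3. The weaker label, potentially effective, applies "if the experimental group improves more than the control group on at least one of the outcome measures", at any of T1, T2 or T3.

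**Which outcomes are primary.** Section 8.1 counts three primary outcomes (RESE, CVTRQ, AVL-AV). Section 8.1.1 then names regulatory emotional self-efficacy as the primary outcome and describes aggression as secondary.

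**Correction.** Under Research objective 1, section 10.1 attaches a Bonferroni correction to LSD post-hoc tests of between-group differences and of change over time. It does not say which tests form the family and does not mention the three outcomes.

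**Sample size.** Section 4.4 targets the primary outcomes at T3 and assumes "an independent two-sided t-test as method of analysis", with the 5% level undivided.

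**The concern.** Under the 10.1 rule the module has three chances to earn the positive verdict at T3, and the plan does not state how those chances are paid for. A verdict that can be reached through any of three tests is wrong more often than one that rests on a single test at the same level.

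The conflict with 8.1 adds to this. A trial with one significant T3 outcome would be effective under 10.1 and only potentially effective under 8.1, so the conclusion could be chosen after the data are seen. Under 10.1 a result on AVL-AV alone would also suffice, although 8.1.1 explains that aggression was not selected as primary.

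**Working it through.** **Inputs.** Alpha 0.05 (10.1). Two-sided test (4.4, the only place where sidedness is given). Effect size: "The analysis was conducted with a moderate effect size of 0.5". Number of outcomes: 3 (8.1). Correlation between outcomes: not given, so it is an assumption and a range is shown.

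**Step 1: reproduce the plan's figure.** A two-sample t-test with d = 0.5, two-sided alpha 0.05 and power 0.80 needs 63.77, so 64 per arm; power at 64 is 80.1%. This matches "This analysis showed that 64 patients need to be included in each condition". Total 2 × 64 = 128, and 128 × 1.2 = 153.6, so 154. The 80% therefore holds for one outcome tested at an undivided 0.05.

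**Step 2: false effective verdict under the 10.1 rule, each T3 contrast at an uncorrected 0.05.** The scenario requires improvement, so only the favourable tail counts, 0.05 / 2 = 0.025 per outcome.
- One outcome: 2.5%.
- Any of three, independent: 1 − 0.975³ = 7.3%. The bound without any assumption on correlation is 3 × 2.5% = 7.5%.
- Any significant T3 result in either direction, independent: 1 − 0.95³ = 14.3%.

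For correlated outcomes, by simulation of multivariate normal test statistics (4 million draws):

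| Assumed correlation | False effective, any of three | Any significant T3 result, either direction | False effective, all three (8.1 rule) |
|---|---|---|---|
| 0 | 7.3% | 14.3% | 0.001% |
| 0.3 | 6.8% | 13.6% | 0.04% |
| 0.5 | 6.3% | 12.5% | 0.16% |
| 0.7 | 5.5% | 11.0% | 0.44% |
| 0.9 | 4.2% | 8.4% | 1.1% |

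**Step 3: what the Bonferroni wording could do.** The answer depends on the family.
- Contrasts within one time point: with two arms there is one between-group contrast, so nothing changes and the table stands.
- Three follow-up times within each outcome: each T3 test runs at 0.05 / 3 = 0.0167. Across three independent outcomes, any significant result is 1 − (1 − 0.0167)³ = 4.9%, and in the favourable direction 1 − (1 − 0.00833)³ = 2.5%. Power at 64 per arm and d = 0.5 is then 65.6%, so the 80% in 4.4 no longer applies.

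**Step 4: cost of correcting across outcomes.** At the first Holm step the level is also 0.0167.
- Power at 64 per arm, d = 0.5: 65.6%.
- With baseline adjustment and an assumed T0–T3 correlation of 0.5, the standardised effect is 0.5 / √(1 − 0.5²) = 0.577 and power is 79.8%.
- Without that adjustment, 80% power needs 85.2, so 86 per arm (172 completers). The plan's own inflation gives 172 × 1.2 = 206.4, so 207; dividing by 0.8 gives 215.

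**The case against.** The strongest reply is that the plan is not silent on multiplicity. It names a Bonferroni correction, and Step 3 shows one reading that brings the T3 error to the single-test level. That reading is possible. It is not stated, though, and it would control the error across outcomes only because there happen to be three follow-up times and three outcomes. LSD with Bonferroni is also a contradiction in terms, because LSD means unadjusted. So 7.3% is a conditional ceiling, not a settled property of the plan.

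A second reply is that the group-by-time interaction acts as a gate. If T3 contrasts were read only after a significant interaction, a simulation with equal time correlations of 0.3 to 0.7 gives at most about 5.5% for any of three independent outcomes, or 2.8% in the favourable direction. The plan states no such gate. It says the post-hoc tests add insight, and it does not name the test that decides the verdict.

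A third reply is that 8.1 demands all three outcomes. Under that rule there is no inflation, as the last column of the table shows. This stands as far as 8.1 goes, but 10.1 says the opposite, so it exposes the conflict and does not answer the point.

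A reader might also infer that a useless module is declared effective 14% of the time instead of 5%. The documents do not support that. The 14.3% includes results that favour control, which 10.1 does not call effective. The matching pair is 7.3% against 2.5%.

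**Conclusion.** The point holds in a limited form. The plan has two incompatible rules for the same verdict, and the more lenient one lets any of three outcomes decide with no stated correction across them. If each T3 contrast is tested two-sided at an uncorrected 0.05, a false effective verdict has probability up to 7.3% against 2.5% for one outcome. That is about 2.9-fold with independent outcomes and 2.5-fold at correlation 0.5; the excess shrinks as correlation rises (4.2% at 0.9). The correlations are assumptions. Under the most favourable reading of the Bonferroni wording the excess disappears, but so does the planned power.

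A reader might go further and infer that one lucky outcome would end the need for research or would drive implementation. The text does not say this. Only the all-three scenario removes the need for further research, and even there replication stays desirable; the one-or-two scenario asks for more research. Section 11.4.1 presents implementation as something that evidence of effectiveness may encourage, not as a consequence that follows.

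**What to change.** 1. Write one rule for effective and use it word for word in 8.1 and 10.1.
2. State whether all three outcomes are primary, and align 8.1 and 8.1.1.
3. If one of three is to suffice, require a favourable between-group contrast at T3 that is significant after Holm correction over the three outcomes (smallest p ≤ 0.0167, next ≤ 0.025, last ≤ 0.05). Name that contrast in 10.1 as the deciding test.
4. Treat T1 and T2 as supportive estimates with 95% confidence intervals and no verdict of their own.
5. Replace the LSD-with-Bonferroni sentence with a statement of which tests, if any, it still covers.

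**Cost.** The analysis text changes, and so must section 4.4. With 64 per arm and d = 0.5 on a single outcome, power at the first Holm step is 66% instead of 80%. Adjusting the T3 contrast for baseline would restore about 80% if the T0–T3 correlation is 0.5; that correlation is an assumption, and this adjusted contrast is not in the current plan. Otherwise the sponsor either accepts 66% openly or enlarges the trial to 86 completers per arm. The choice should be recorded before the data are analysed.

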### ***Secondary objectives***

The secondary objectives are:

1. To determine if there is more improvement in improvement regulatory emotional self-efficacy, treatment readiness, and aggression in the experimental than control group during, directly after completing, and three months after completing the internet-based intervention 'Aggression'.
2. To determine if there is more improvement on dynamic risk in the experimental than the control group after completing the internet-based intervention 'Aggression'.
3. To determine if the number of face-to-face treatment contacts over a period of 37 weeks is lower in the experimental than the control group.
4. To determine if the level of engagement with the intervention measured at the beginning, halfway and at the end of the internet-based intervention Aggression, and the adherence to the intervention, is a predictor for effectiveness.
5. To map experiences with the internet-based intervention Aggression of forensic psychiatric patients that followed (part of) the intervention.
6. To map experiences with the internet-based intervention Aggression of therapists that used the intervention in at least five patients.

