### **8.1.1 Main study parameter/endpoint**

#### ***Regulatory emotional self-efficacy – RESE***

A main advantage that is reported in qualitative studies on the use of internet-based interventions in forensic psychiatry, is that patients are working on part of their treatment independently. On top of TAU, internet-based interventions offer additional exercises and information to support the patient in dealing with their undesired aggressive behaviour. This is expected to provide them with more insights and tools to improve their aggression regulation than patients who do not follow an internet-based intervention outside of in-person treatment sessions. It is thus expected that the self-efficacy of patients that follow an additional internet-based intervention will increase more than in TAU. In other words: because they receive additional treatment via the intervention and work on it independently, their confidence in regulating their own emotions can increase.

Consequently, the primary outcome measure of this study is regulatory emotional self-efficacy. This construct is measured by means of the validated, 12-item Regulatory Emotional Self-efficacy (RESE) scale [31]. The RESE scale assesses self-efficacy in managing negative emotions (8 items) and in expressing positive emotions (4 items). Negative emotional self-efficacy refers to the perceived “capability to ameliorate negative emotional states once they are aroused in response to adversity or frustrating events and to avoid being overcome by emotions such as anger, irritation, despondency, and discouragement” [31]. Positive self-efficacy is defined as the perceived capability “to experience and to allow oneself to express positive emotions such as joy, enthusiasm and pride in response to success or pleasant events” [31]. Earlier research has demonstrated the validity and reliability of the RESE scale [31, 43, 44]. Because the RESE scale consists of only 12 items, it is easy to administer and does not require much effort of participants.

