### ***Aggression – AVL-AV***

The main objective of forensic psychiatric treatment is to prevent (re)offending. Consequently, preventing aggression is an important goal of the entire treatment program. However, reaching this goal, even by means of long and intensive therapy has proven to be difficult. We did not select aggression as a primary outcome measure because a direct impact on changes in aggression might be too much to expect from an internet-based intervention. However, it might be that patients that the expected changes in self-efficacy due to the internet-based intervention result in actual behaviour change, so self-reported aggression is used as a secondary outcome. Self-reported aggression is assessed by means of the Dutch version of the much-used and validated Aggression Questionnaire (Aangepaste Versie van de Agressie Vragenlijst; AVL-AV) [33, 34]. The 12 items of the questionnaire are divided into four subscales: physical aggression, verbal aggression, anger, and hostility. The AVL-AV had been shown to be reliable and valid in earlier research and is easy to administer because it consists of only 12 items.

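### Sections 8.1 and 10.1 give opposing verdicts for a win at T3 on one or two outcomes, and the plan does not settle which outcomes are primary

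*Combined protocol and SAP*

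**What the plan says.** **Verdict rule.** Section 8.1 has two tiers. A gain over control on at least one outcome at T1, T2 and/or T3 makes the intervention potentially effective. The higher tier reads: "The intervention is viewed as effective in case of changes on all three outcome measures on T3". Section 10.1 (Determining effectiveness) goes through scenarios. For a T3 gain on one or two outcomes it says: "In that case, the intervention is viewed as effective since it leads to benefits on the long term". A gain on all three at T3 is also called effective; the difference is that further research is then no longer required.

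**Primary status.** Section 8.1 says: "To answer the first research question, three primary outcome measures will be used". Section 10.1 also speaks of three primary outcomes, and the Summary builds the primary objective on the same three. Section 8.1.1 says under RESE: "Consequently, the primary outcome measure of this study is regulatory emotional self-efficacy". Under AVL-AV it explains that aggression was not chosen as primary, "so self-reported aggression is used as a secondary outcome". In section 2 the three outcomes appear as the first of the secondary objectives: "To determine if there is more improvement in improvement regulatory emotional self-efficacy, treatment readiness, and aggression in the experimental than control group".

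**Alpha and power.** Section 4.4 sizes the trial at 64 per arm for d = 0.5 with 80% power and 5% alpha, using "an independent two-sided t-test as method of analysis". Section 10.1 says "significance was accepted at 0.05 or lower" and adds a Bonferroni correction to the post-hoc t-tests that follow the mixed model. It does not say which tests form the family.

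**The concern.** If only RESE improves at T3, section 8.1 gives potentially effective and section 10.1 gives effective. Section 8.1 does not use the word 'only', but its lower tier explicitly includes T3. If one T3 win were enough for 'effective', that tier would have no meaning at T3. Section 10.1 is not a refinement of 8.1 either, because it gives the same label to one, two or three wins.

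The trial is unblinded and no text takes precedence, so the headline verdict could be chosen after the results are known. The two rules also behave very differently. Any-of-three wins easily, but its false-positive rate is inflated if each test is run at 0.05. All-three has no inflation, but its power is well below the 80% that section 4.4 implies. The unclear primary status makes this worse, because a reader cannot tell which outcomes count towards either rule.

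**Working it through.** **1. Side by side, results at T3**

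| Outcomes won at T3 | Section 8.1 | Section 10.1 |
|---|---|---|
| 1 or 2 | potentially effective | effective |
| 3 | effective | effective |

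The rules part exactly when one or two outcomes win at T3.

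**2. The plan's own figure.** Inputs from section 4.4: d = 0.5, n = 64 per arm, two-sided 0.05. Noncentrality is d × √(n/2) = 0.5 × √32 = 2.83 on 126 degrees of freedom. Exact t-test power is 0.801 (0.795 with 63 per arm), so 64 per arm reproduces. It is the power of one test on one outcome.

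**3. Closed-form results if the outcomes are uncorrelated, 0.05 per test**
- Any-of-three false positive, two-sided: 1 − 0.95³ = 0.143
- Any-of-three false positive favouring the intervention: 1 − 0.975³ = 0.073, against 0.025 for one test
- Any-of-three power: 1 − (1 − 0.8015)³ = 0.992
- All-three power: 0.8015³ = 0.515
- Exactly one or two wins: 0.992 − 0.515 = 0.477

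At 0.05/3 = 0.0167 per test, single-outcome power is 0.656 and the any-of-three two-sided error is 1 − (1 − 0.05/3)³ = 0.049.

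**4. Correlated outcomes.** The documents give no correlation, so 0 to 0.7 is an assumption. Each setting used 400,000 simulated trials with three equally correlated t statistics on 126 degrees of freedom. Power rows take d = 0.5 on all three outcomes and count wins favouring the intervention.

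| Quantity | Corr. 0 | 0.3 | 0.5 | 0.7 |
|---|---|---|---|---|
| Exactly one or two wins, 0.05 | 0.478 | 0.400 | 0.338 | 0.261 |
| Exactly one or two wins, 0.0167 | 0.677 | 0.553 | 0.461 | 0.352 |
| Any-of-three false positive, two-sided, 0.05 | 0.142 | 0.136 | 0.127 | 0.109 |
| Any-of-three false positive, favourable, 0.05 | 0.073 | 0.069 | 0.063 | 0.054 |
| Any-of-three power, 0.05 | 0.992 | 0.972 | 0.951 | 0.921 |
| Any-of-three power, 0.0167 | 0.959 | 0.912 | 0.873 | 0.825 |
| All-three power, 0.05 | 0.514 | 0.573 | 0.613 | 0.660 |
| All-three power, 0.0167 | 0.283 | 0.359 | 0.413 | 0.474 |

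**5. Only one outcome truly responds (d = 0.5).** At 0.05 the any-of-three rule wins in 80% to 81% of trials and the all-three rule in under 1%. The verdicts therefore differ in about 80% of trials.

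**6. Holm across the three T3 tests at two-sided 0.05.** With d = 0.5 on all three, the chance of at least one win is 0.959 to 0.825 and per-outcome power is 0.750 to 0.728. With one responding outcome, power is about 0.66. Restoring 80% for one test at 0.0167 would take 86 per arm.

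**The case against.** The strongest objection is that inflation is not established. Section 10.1 does promise a Bonferroni correction on the post-hoc between-group t-tests. If its family has three or more tests, each runs at 0.0167 or less and the any-of-three error at T3 is at most 4.9%. That is right as far as it goes: the 14% to 11% applies only if T3 is judged at 0.05 per test. But the family is undefined, so the level behind the T3 verdict cannot be determined. The correction would not reconcile the two labels either. At 0.0167 the disputed zone widens to 68% to 35% when all three outcomes respond.

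Other points carry some weight:
- The main analysis is a mixed model, and section 8.1.1 itself doubts a direct effect on aggression. The percentages are therefore illustrative. The contradiction does not depend on them.
- With 20% drop-out, 154 × 0.8 / 2 = 61.6 per arm remain. Power for one test is then about 0.786 at 0.05 and 0.636 at 0.0167, slightly below the figures for 64.
- Listing the three outcomes under the secondary objectives in section 2 may be loose structure, since those items spell out a general primary objective. It is weaker evidence than the conflict within section 8.1.1.
- Section 10.1 still asks for more research after one or two wins, so the practical messages partly converge. The stated conclusion still differs.

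**Conclusion.** The concern holds. The conflict between sections 8.1 and 10.1 is literal, primary status is inconsistent, and no text says which prevails. It must be fixed before results are seen, because the affected result is a likely one: 48% to 26% of trials at 0.05 per test if all three effects are 0.5, and about 80% if only one outcome responds. Those figures assume T3 t-tests with 64 per arm and correlations of 0 to 0.7. A higher correlation narrows the disputed zone without closing it: with all three effects at 0.5, a normal-approximation simulation at 0.05 per test and correlation 0.9 still gives about 15%. The plan states neither the error rate nor the power of either rule.

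**What to change.** Adopt one rule, worded identically in sections 8.1 and 10.1, and one primary set throughout.

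- **Option A: three primaries**, in line with the Summary and with the count in sections 8.1 and 10.1. Apply Holm at two-sided 0.05 across the three T3 between-group tests. Call the intervention effective if at least one is significant in its favour, and report which. This replaces section 8.1's all-three rule.
- **Option B: RESE at T3 as the single primary** at 0.05, in line with section 8.1.1 under RESE, with CVTRQ and AVL-AV secondary.

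Carrying section 8.1's two tiers into section 10.1 would also be consistent, but 'effective' would then have only 51% to 66% power at 0.05 per test, under the assumptions above.

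Whichever rule is chosen:
- name the test that decides T3, for example the mixed-model between-group contrast at T3;
- state the Bonferroni family, or replace it with the chosen procedure;
- treat T1 and T2 as supportive;
- align section 2 and section 8.1.1 with the chosen set;
- restate power in section 4.4 for the chosen rule. For option A with 64 per arm and all effects at 0.5, that is 96% to 83% for at least one win and 75% to 73% per outcome; it is about 66% if only one outcome responds. State the number expected after drop-out as well.

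**Cost.** Wording only, with no larger sample. Option A shows less favourable power when a single outcome responds; the 86 per arm that would restore 80% is not proposed. Under option B, a win on CVTRQ or AVL-AV alone no longer earns 'effective'.
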